**TABLE 1: Hypotheses and measures associated with Study 1**

Hypothesis	Method of Measurement/Testing
Decreased BMI	Body mass (weight) at baseline, treatment midpoint, post-treatment, and at 8 week post-treatment follow-up
Changes in BMD	DXA at baseline, post-treatment, and at 8 week post-treatment follow-up
Improved bowel and bladder function	Self-report at baseline, treatment midpoint, post-treatment, and at 8 week post-treatment follow-up
Reduced spasticity	MAS and SCI-SET at baseline, treatment midpoint, post-treatment, and at 8 week post-treatment follow-up
Reduction in pain	Self-report at baseline, treatment midpoint, post-treatment, and at 8 week post-treatment follow-up
Enhanced well-being	Self-report at baseline, treatment midpoint, post-treatment, and at 8 week post-treatment follow-up
Neurological recovery (complete SCI)	ASIA neurological exam and FR at baseline, treatment midpoint, post-treatment, and at 8 week post-treatment follow-up
Neurological recovery (incomplete SCI)	ASIA neurological exam, FR, and MMT at baseline, treatment midpoint, post-treatment, and at 8 week post-treatment follow-up
Functional recovery (poorly-ambulatory)	FR, MMT, FIM-G, WISCI-II, TUG, 10MWT, and BRPE at baseline, treatment midpoint, post-treatment, and at 8 week post-treatment follow-up
Community mobility	FIM-G, WISCI-II, TUG, 10MWT, and 6MWT and BPPE relative to published recommendations for community ambulation

## 7.0 Risks of Investigational Devices

### Risks:

See section 3 of this document. As stated in that section, following over 1200 hours of exoskeleton walking with 40 subjects with SCI, no serious adverse events occurred. As such, risks to subjects are expected to be minimal.

### Potential benefits:

The intent of the study is to characterize potential health and mobility benefits provided by the exoskeleton. As such, there is no clearly-established medical evidence of health benefits resulting from exoskeleton walking. Despite this, the investigators hypothesize that subjects will experience improvements in well-being, circulation, bowel and bladder function, skin integrity, and sleep, in addition to reductions in spasticity and pain. Moreover, subjects with incomplete SCI may experience neurological and/or functional improvement.

Regarding the general population of individuals with SCI, if exoskeleton use substantially mitigates the prevalence of secondary impairments, as hypothesized herein, these devices could substantially decrease the cost of health care for individuals with SCI. If such use is found to facilitate neurological and/or functional recovery for patients with motor-incomplete injuries, the intervention could have a substantial impact on improving rehabilitative outcomes for large numbers of individuals.

## **8.0 Clinical Monitoring Plan and Reporting of Adverse Events**

Good clinical practice monitoring: Each site will employ an independent medical monitor, who will review the study protocol prior to each study; observe the initial treatment session of the first subject in each study; and be apprised of any AE at any site in the study.

Safety monitoring: Safety monitoring and oversight will be performed by each respective site PI. All PIs will have the authority temporarily or permanently to discontinue a particular protocol and/or the involvement of a given subject, if deemed necessary or appropriate for the safety of the subject. If any concern or unexpected issue is identified with one subject that could be of potential risk or concern to other subjects, action will be taken by the data and safety monitoring team to address, mitigate, and/or eliminate such risk from the study. Any AE will be reported immediately, i.e., within 24 hours, to the site study coordinator and site PI. The site PI and site medical monitor will determine if any action is required to resolve the AE. The site PI will also report the AE to the site IRB, and to the lead site study coordinator and PI.

Risk management and emergency response:

Risks will be managed by employing the following safety and oversight measures:

- A licensed PT will directly supervise all sessions.
- A safety gait belt or overhead harness will be utilized at the discretion of the supervising PT.
- Blood pressure and heart rate will be monitored throughout each session to ensure vital signs fall within the recommended ranges for locomotor training activity.

Any AE will be reported immediately, i.e., within 24 hours to the site study coordinator and site PI. The site PI and site medical monitor will determine if any action is required to resolve the AE. The site PI will also report the AE to the site IRB, and to the lead site study coordinator and PI. Each site PI will have the authority to temporarily or permanently discontinue a particular protocol and/or the involvement of a given subject, if deemed necessary or appropriate, for the safety of the subject. If any concern or unexpected issue is identified with one subject that could be of potential risk or concern to other subjects, the data and safety monitoring team will take action to address, mitigate, and/or eliminate such risk from the study.

If determined by study personnel or the medical monitor that an injury occurred as a direct result of the tests or treatments involved in this study, each respective site will cover the cost of immediate medical care provided at that site to treat the injury. Neither the study, nor each site, will be responsible for the costs of additional care.

## **9.0 Study Withdrawal/Discontinuation**

Subjects can choose to discontinue participation in the study at any time. If the investigators feel that the safety of the participant, or others, is compromised for any reason during the study, that subject will be withdrawn from the study.

## **10.0 Privacy/Confidentiality Issues**

All data, dexa scans, videos, and photographs recorded during this study will be held in a secured location at the trial site. Data will continue to be held until the study researchers deem the data is no longer scientifically relevant, at which point the data will be destroyed. All data will be de-identified prior to publication.

The research team will take photographs and record videos of participants throughout this study. The participants entire body including their face will be included. The purpose of the photographs and videos is to help participants

learn more about the device as well as to provide information to the researchers and for other participants in this or other studies. The photographs and videotapes may also be used for scientific publications, meetings of scientists, public formats for nonscientific groups. Participants will be given the option to have or not have their photographs or videos shared outside of this study. Photographs and videos will be securely stored at the participants site. If participants have agreed to allow photographs or videos shared outside of this study they will be transferred using Vanderbilt's secure file transfer or via RedCap.

## **11.0 Follow-up and Record Retention**

The data collected in the study will be maintained in a RedCap database. Key study personnel at each site will have a user id and password and will have access to only their data. Vanderbilt will have access to all data at all sites. Data will continue to be held until the study researchers deem the data is no longer scientifically relevant, at which point the data will be destroyed.

Statistical Analysis Plan

Mobility and Therapeutic Benefits resulting from Exoskeleton Use in a Clinical Setting (SC140121 Study 1)

NCT03082898

[name]

H. Fort Flowers Professor of Mechanical Engineering

Professor of Electrical Engineering

Professor of Physical Medicine and Rehabilitation

[name]

[name]

[name]

Statistical Analysis Plan

Normality of data was determined for each measure by a Kolmogorov–Smirnov (KS) test. All measures were determined to be non-normally distributed, and as such are represented by median and IQR rather than mean and standard deviation. Differences in medians in all measures were tested using a Wilcoxon rank-sum test, with confidence levels for each given by corresponding p values.

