## 6.0 Study Procedures

### Design:

This study will include 24 non-ambulatory or poorly-ambulatory individuals with chronic SCI, i.e., at least 6 months post-injury, 12 with complete and 12 with incomplete SCI, to assess the mobility and therapeutic benefits resulting from exoskeleton use in a clinical setting. Changes in physiological and neurological status will be assessed via measurements taken pre-, mid-, and post- the 8-week intervention, as well as 8 weeks post-treatment. At all study sites, subject enrollment will begin following IRB approval, with 8 subjects enrolled at each of the 3 sites. Following IRB approval and enrollment, the study is expected to occur over an 18-month period. The treatment for each subject will consist of 31 sessions spanning 18 weeks in total, comprising a combination of 4 assessment, 3 training, and 24 treatment sessions. The 24 treatment sessions each consists of approximately 1 hour of walking in the exoskeleton, although 1.5 hours are allotted to account for donning/doffing, measurement of vital signs, skin checks, etc., and will be delivered 3 times per week over an 8-week period.

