In addition to assessment of health, neurological and functional status, additional assessments will be performed to characterize the level of mobility provided by the exoskeleton. These assessments include the FIM-G, WISCI-II, 10MWT, 6MWT, TUG, and BRPE tests, all performed while the subject is wearing the exoskeleton. The battery of mobility assessments will occur within the standard treatment sessions at treatment midpoint (i.e., after 4 weeks of treatment, during sessions 15 and 16) and at treatment end (i.e., after 8 weeks of treatment, during sessions 28 and 29). Note that the TUG test is performed on a separate day from the other assessments, to mitigate the number of tests to complete in a single session. Note also that the 10MWT will be administered once during each quarter of treatment, since the test is informative and easily administered, and thus will not substantially disrupt a session of typical exoskeleton treatment.

The scheduling of assessment for each subject is provided in the chart below.

	Outcome Measure	Baseline	Fitting and Training	Treatment (12 sessions)												Mid-treatment	Treatment (12 sessions)															
				Treatment (12 sessions)														Treatment (12 sessions)														
Health effects	DXA																															
	MAS																															
	SCI-SET																															
	Weight																															
	Bloodwork																															
	Self-report																															
Neurological recovery	Neuro exam																															
	FR																															
Neurological recovery for poorly-ambulatory	FIM-G w/o Exo																															
	WISCI-II w/o Exo																															
	10MWT w/o Exo																															
	TUG w/o Exo																															
Mobility (in exoskeleton)	FIM-G																															
	WISCI-II																															
	10MWT																															
	6MWT																															
	TUG																															
Other	BRPE																															
	Steps																															
	Skin																															
	Vital signs																															
	Total session	1	2	3	4	5	6	7	8	9	10	11	12	13	14	15	16	17	18	19	20	21	22	23	24	25	26	27	28	29	30	31
	Total week	1	2	2	2	3	3	3	4	4	4	5	5	5	6	6	6	7	7	7	8	8	8	9	9	9	10	10	11	11	18	
	Treatment session																															
	Treatment week	1	1	1	2	2	2	3	3	3	4	4	4	4	5	5	5	6	6	6	7	7	7	8	8	8	8	8	8	8		

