#### Data Analysis

Table 1 lists the relationships between the outcome measures and each hypothesis. Given that each patient is in a chronic stage of injury (i.e., spontaneous changes in health and neurological status are unlikely or minimal), the investigators assume that any statistically significant change in the outcome measures between pre- and post-treatment will have resulted from treatment. Since all measures are quantitative, including the self-report and SCI-SET, testing the respective hypotheses entails testing the extent to which the pre- and post-treatment means, of respective measurements across all subjects, are different. As such, the investigators will employ paired-sample t-tests to test the extent to which pre- and post-treatment means are statistically different, by employing a 95% confidence level in the analysis, unless results indicate a more appropriate confidence level for a given set of data. In addition to using paired t-tests for validating differences in means, and establishing associated confidence levels in those differences, analysis of variance (ANOVA) methods will be employed when determining statistical significance of differences in means between multiple data sets, with 95% confidence levels. Specifically, ANOVA will be used when assessing differences in means between pre-, mid-, post-, and 8-week follow-up measurements. In addition to analyzing results across all subjects, more meaningful results will be provided by separating the subject population into appropriate groups, such as: motor-complete and motor-incomplete individuals; non-ambulatory and poorly-ambulatory ones; individuals with tetraplegia and those with paraplegia; persons with upper paraplegia and those with lower paraplegia; etc. For example, measures associated with walking while not wearing the exoskeleton will only be recorded for poorly-ambulatory individuals; neurological recovery is not expected for individuals with motor-complete injuries (while perhaps possible, such recovery is not hypothesized here); and individuals with tetraplegia are less likely to achieve walking speeds and levels of independence commensurate with community ambulation, relative to individuals with paraplegia. For these groups, ANOVA techniques will be employed to assess differences in

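### The SAP names an independent-samples rank-sum test for every measure, although the main comparison is within subject and the protocol plans a paired test

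*SAP*

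**What the plan says.** The SAP is one short paragraph. It reports a Kolmogorov–Smirnov check of each measure and concludes: "All measures were determined to be non-normally distributed, and as such are represented by median and IQR rather than mean and standard deviation". It then names its only test: "Differences in medians in all measures were tested using a Wilcoxon rank-sum test". It does not say which visits or groups were compared, and it mentions no paired or repeated-measures method.

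The protocol describes a within-subject design. Section 6.0, Design, says: "Changes in physiological and neurological status will be assessed via measurements taken pre-, mid-, and post- the 8-week intervention", with a further measurement 8 weeks after treatment ends. Table 1 lists the same visits for nearly all the health and recovery hypotheses (DXA omits the midpoint).

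For the pre/post comparison, the Data Analysis section says "the investigators will employ paired-sample t-tests to test the extent to which pre- and post-treatment means are statistically different". Across visits, "ANOVA will be used when assessing differences in means between pre-, mid-, post-, and 8-week follow-up measurements"; a repeated-measures form is not specified. The same section also plans ANOVA between independent subgroups, such as motor-complete and motor-incomplete subjects.

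**The concern.** The rank-sum test takes its null variance from two unrelated samples. Pre and post values from the same people are not unrelated. If they are positively correlated, the test overstates the variance of the difference and its p values are too large.

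Non-normality does not explain the choice. The usual rank counterpart of a paired t-test is the signed-rank test, which keeps the pairing. What matters for a paired test is the distribution of each subject's change, and the SAP reports normality only for the measures themselves.

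The stakes are high for this design. There is no control arm, and the protocol attributes any significant pre-to-post change to treatment. The within-subject comparison therefore carries almost all of the health and recovery hypotheses. An underpowered test could make a real change look like no effect.

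**Working it through.** The documents give no power calculation, SD, effect size or correlation, so there is no figure of the plan's to reproduce. The size of the problem is computed over a range.

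**Inputs from the protocol:** n = 24, with 12 motor-complete and 12 motor-incomplete (Study Outline; Design); 95% confidence level (Data Analysis).

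**Assumptions:** two-sided 5%; all pairs complete; equal pre and post SD; correlation ρ from 0 to 0.9; shifts d of 0.3, 0.5 and 0.8 between-subject SD.

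**Step 1, closed-form approximation.** For independent samples the variance of the mean difference is 2σ²/n. For paired data it is 2σ²(1−ρ)/n. An unpaired test therefore uses a standard error too large by a factor 1/√(1−ρ). With Φ the normal distribution function:

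- true type I error of the unpaired test = 2[1 − Φ(1.96/√(1−ρ))]
- power of the unpaired test = 1 − Φ((1.96 − d√(n/2))/√(1−ρ))
- power of the paired test = Φ(d√(n/(2(1−ρ))) − 1.96)

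For n = 24, d = 0.5, ρ = 0.7:

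- type I error: 1.96/√0.3 = 3.58, giving 0.00035, or about 0.04%
- unpaired power: (1.96 − 0.5√12)/√0.3 = 0.228/0.548 = 0.416, giving 0.34
- paired power: 0.5√(24/0.6) − 1.96 = 1.20, giving 0.89

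For n = 12 at the same d and ρ, the powers are 0.09 and 0.61. At ρ = 0 and n = 24 both formulas give 0.41.

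**Step 2, simulation of the rank tests themselves** (normal data, n = 24, 20,000 trials per cell):

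| Correlation | 0 | 0.3 | 0.5 | 0.7 | 0.8 | 0.9 |
|---|---|---|---|---|---|---|
| Rank-sum type I error, % | 4.9 | 2.1 | 0.8 | 0.1 | 0.02 | <0.01 |
| Power, 0.3 SD: rank-sum | 0.16 | 0.12 | 0.09 | 0.06 | 0.04 | 0.02 |
| Power, 0.3 SD: signed-rank | 0.16 | 0.21 | 0.28 | 0.43 | 0.59 | 0.87 |
| Power, 0.5 SD: rank-sum | 0.37 | 0.35 | 0.34 | 0.31 | 0.30 | 0.28 |
| Power, 0.5 SD: signed-rank | 0.36 | 0.49 | 0.63 | 0.84 | 0.95 | 1.00 |
| Power, 0.8 SD: rank-sum | 0.75 | 0.79 | 0.82 | 0.87 | 0.91 | 0.95 |
| Power, 0.8 SD: signed-rank | 0.74 | 0.87 | 0.95 | 1.00 | 1.00 | 1.00 |

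A separate run of 5,000 trials per setting gave signed-rank type I error between 4.3% and 5.2% for ρ from 0.3 to 0.8.

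**Step 3, share of power lost** = 1 − rank-sum/signed-rank. At 0.5 SD: 1 − 0.34/0.63 = 46% at ρ = 0.5, and 1 − 0.31/0.84 = 63% at ρ = 0.7. At 0.8 SD the loss is about 5–14% for ρ of 0.3 or more.

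**Step 4, smaller sets** (0.8 SD, ρ = 0.7). For n = 12, one AIS stratum: 0.42 against 0.88, a loss of 1 − 0.42/0.88 = 52%. For n = 8: 0.20 against 0.64, a loss of 69%. The n = 8 case is illustrative. The Data Analysis section says "measures associated with walking while not wearing the exoskeleton will only be recorded for poorly-ambulatory individuals", but the protocol does not say how many such subjects there will be.

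**Step 5, non-normal data** (n = 24, 0.5 SD on the underlying scale, ρ = 0.7). Log-normal: 0.31 against 0.78. Five-level ordinal, with 23–47% zero changes across the correlations tried and zeros dropped: 0.28 against 0.71. The pattern does not depend on normality.

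**The case against.** The SAP names no contrasts, so it is not proved that rank-sum was applied to pre/post change. The word may be a slip for signed-rank, in which case the p values stand. Rank-sum is also a sound choice for the independent subgroup comparisons in the protocol. All of this is true. But the sentence covers all measures and is the only test named, so on its face the plan has no suitable test for its main comparison, and a reader cannot tell what was done.

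The pairing issue also does not reach every measure in the same way. For in-exoskeleton mobility, "The battery of mobility assessments will occur within the standard treatment sessions at treatment midpoint" and again at the end of treatment, so there is no pre-treatment value, and Table 1 judges those results "relative to published recommendations for community ambulation". Only a midpoint-to-end comparison would be within subject there.

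The error is conservative under positive correlation, so a significant rank-sum result is not undermined by it. The p values are better called miscalibrated than worthless. The protocol has no power target to breach, and with 24 subjects and a 0.8 SD shift the loss is modest. These points limit the damage to non-significant results, chiefly for modest effects, highly correlated measures and small subsets. They do not make an unpaired test right for paired data.

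**Conclusion.** The concern holds. The test named in the SAP does not fit within-subject change, and the stated reason of non-normality does not justify dropping the protocol's pairing. That much is certain from the text; whether the analysis itself was unpaired is not.

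If it was unpaired, then at n = 24 and 0.5 SD nothing is lost at correlation 0, just under half the power at 0.5, and about 63% at 0.7. In a stratum of 12 with a 0.8 SD shift and correlation 0.7, about half is lost. These sizes rest on assumed correlations and effects and on complete pairs. The conservative direction rests on the correlation being positive. A non-significant rank-sum result should not be read as evidence of no benefit.

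**What to change.** 1. Confirm which test was run. If it was signed-rank, correct the word; the pre/post p values need no further change.
2. If it was rank-sum, replace the sentence with wording such as: *Change from baseline (session 1) to post-treatment (session 30) was tested within subjects with the two-sided Wilcoxon signed-rank test; zero changes were handled by [stated method, e.g. Pratt]; the paired change is reported with a Hodges–Lehmann 95% CI.* Add a sign test as a sensitivity analysis where changes are clearly asymmetric.
3. For measures compared across several visits, use a Friedman test, or a mixed model with a subject effect and a distribution suited to the measure. A default Gaussian model would bring back the assumption that the SAP rejects.
4. Keep rank-sum for change scores between independent subgroups, and name those contrasts.
5. For in-exoskeleton mobility, report the median with a 95% CI against the published recommendation, and treat any midpoint-to-end comparison as paired.
6. State the number of complete pairs per measure and how missing visits were handled. Section 9.0 lets subjects withdraw at any time; signed-rank drops incomplete pairs and Friedman drops subjects missing any visit.
7. Explain the departure from the paired t-test. The SAP is written in the past tense, so label any re-run as a correction made after results were known.

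The cost is SAP wording and, if needed, a re-analysis of existing data. Signed-rank assumes roughly symmetric changes and loses information when many changes are zero, as is likely on MAS, FIM-G and WISCI-II. At correlation near 0 it is marginally weaker than rank-sum (0.36 against 0.37 at n = 24, 0.5 SD, normal data).
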